3.5.3 Intervention administration

The injection intervention will be administered at study visit 1 following successful recruitment and consent. Since physical therapy is considered standard of care treatment in the management of pregnancy related PGP, all participants will need to have failed PT.

3.5.4 Follow-up

Patients will be instructed to contact the study nurse coordinator blinded to the study hypotheses with any side effects: flushing, nausea, vomiting, insomnia, and/or worsening pain at any time during the first week. The study nurse coordinator will then contact each patient by phone on day 7 after the injection regarding medication tolerance. After the four weeks of physical therapy, patients will return for a repeat questionnaire administration and physical examination. Questionnaires will be performed prior to physical examination so as not to

Protocol Version 4 – 03-06-2015

influence pain scores. During the course of physical therapy, they will be reminded by the physical therapist to follow-up with study visit 2 and reminder letters mailed the week prior to study visit 2. Study visit 3 will be performed eight weeks post injection to determine if the intervention has a lasting effect. Study visit 4 will occur 6 weeks post-delivery and will include the same questionnaires and physical examination to determine if any chronic pain remains.

3.5.5 Adverse event reporting*

The PI or the study nurse coordinator can be reached by pager or phone and will be on call for study patients 24 hours a day. [name], chief Loyola Maternal Fetal Medicine will also be available for patient adverse reactions. Adverse events to be recorded will include excessive bleeding, infection, significantly worse pain at the 7 day post-injection phone check, fetal distress or demise, fall post injection, and/or maternal hospital admission. If the subject has persistent post injection side effects of flushing, nausea, vomiting or insomnia, this will be reported. If any other unanticipated adverse event occurs, this will also be immediately reported to the IRB. A data safety monitoring plan is detailed below in the section titled “Safety Monitoring Plan.”

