treatment outweighs the minimal risk. Both study groups will receive standard of care physical therapy (cost covered by their insurance), a proven treatment for pregnancy related pelvic girdle pain. For the intervention group that receives methylprednisolone, expected immediate side effects might include vasovagal reaction and delayed (2 days) side effects might include injection site soreness, sweating or facial flushing³⁰. Toxicity at high levels and multiple dosing effects are not expected given that this is a low dose of corticosteroid injected locally. Infection rates associated with injection are low and typically seen in intraarticular not extraarticular injections³¹. A possible rare adverse effect might include allergic reaction. If an adverse reaction or side effect occurs, the subject will be seen by [name] (maternal fetal medicine) at Loyola. This will also be immediately reported to the IRB.

The benefits of the intervention include the possibility of superior pain relief compared with placebo. Lidocaine has been safely and successfully used in pregnant women undergoing amniocentesis.³² Oral steroids are used for other conditions in pregnancy such as asthma, rheumatoid arthritis, and severe sinusitis. They are also utilized in the treatment of pre-term labor to assist in the development of fetal lung maturity. Methylprednisolone is a class B drug and its well-established clinical utility in other diseases lends to the safety of its potential use in this debilitating pain condition (PGP) in pregnancy and warrants further study for the treatment of musculoskeletal pain.

I. Safety Monitoring Plan

a. Definition of adverse events, serious adverse events

- i. An adverse event is defined as any symptom or medical problem experienced by the participant following consent to participate. All adverse events must be reported to the study physician and regulatory coordinator within three working days of discovery. All adverse events that occur during the trial will be recorded on the adverse event log. The investigator study physician will ask patients at each visit "Have you experienced any

symptoms or medical problems since your last visit?” and will subsequently record all events using the adverse event log.

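### Adverse event rules differ between Sections 3.5.4, 3.5.5 and 4 and the Safety Monitoring Plan, so short-lived side effects may be under-ascertained and IRB reporting inconsistent in both arms

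*Combined protocol and SAP*

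**What the plan says.** Five places bear on which events are noticed, logged and passed on.

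- **Section 3.5.4** tells women to contact the nurse coordinator "with any side effects: flushing, nausea, vomiting, insomnia, and/or worsening pain at any time during the first week". It sets no persistence condition. The coordinator then telephones on day 7 about tolerance of the medication.
- **Section 3.5.5** opens with a list: "Adverse events to be recorded will include excessive bleeding, infection, significantly worse pain at the 7 day post-injection phone check, fetal distress or demise", followed by falls and maternal admission. It continues: "If the subject has persistent post injection side effects of flushing, nausea, vomiting or insomnia, this will be reported". No duration is given for persistent, and no recipient is named. Other, unanticipated events go immediately to the IRB. The section ends with a cross-reference, "A data safety monitoring plan is detailed below in the section titled", to the Safety Monitoring Plan.
- **Section 4, Maternal Risk and Benefit**, says of the methylprednisolone group that "expected immediate side effects might include vasovagal reaction and delayed (2 days) side effects might include injection site soreness, sweating or facial flushing", mentions infection as a low risk, and adds: "A possible rare adverse effect might include allergic reaction". Any adverse reaction or side effect is to go to the IRB at once.
- **Safety Monitoring Plan, part a, item i**: "An adverse event is defined as any symptom or medical problem experienced by the participant following consent to participate". All such events go on the log, and the study physician asks an open question about symptoms at each visit.
- **Safety Monitoring Plan, part d, item i** requires prompt IRB notice of serious and unexpected events associated with the project. Unexpected means not listed as a risk in the consent document.

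**The concern.** A brief flush on day 2 is an adverse event under item i, and a woman is asked to phone it in under Section 3.5.4. Under Section 3.5.5 it is reported if it persists, by a standard each staff member must guess. Under Section 4 it goes to the IRB immediately. Under part d it goes only if it is serious or is missing from the consent form's list of risks. No section says which rule prevails.

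The prompts also miss much of what the plan itself expects. Someone working from Sections 3.5.4 and 3.5.5 has no named cue for soreness, sweating, vasovagal reaction or allergic reaction. The catch-all in 3.5.5 covers unanticipated events, and Section 4 has already anticipated these four.

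What is at stake is the completeness of the tolerability data. Section 2.1 says there are no randomized trials of corticosteroids for this condition in pregnancy, so readers will look to this trial's event counts.

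**Working it through.** The plan states no adverse event rate, so there is no figure to reproduce. The check is a comparison of texts, followed by an illustration on stated assumptions.

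**1. Effects named, side by side**

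| Effect | 3.5.4 (women told to report) | 3.5.5 | Section 4 |
|---|---|---|---|
| Flushing | yes | if persistent | yes |
| Nausea, vomiting, insomnia | yes | if persistent | not named |
| Worse pain | yes | if significantly worse at the day-7 call | not named |
| Infection | no | yes, unconditional | yes |
| Vasovagal reaction | no | no | yes |
| Injection-site soreness | no | no | yes |
| Sweating | no | no | yes |
| Allergic reaction | no | no | yes, rare |

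The overlap is flushing and infection. Four effects named in Section 4 have no named prompt in 3.5.4 or 3.5.5. Item i covers every row.

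**2. IRB thresholds.** If the persistence sentence concerns the IRB, there are three rules for a non-serious side effect: persistent cases (3.5.5), every case immediately (Section 4), and only unexpected associated cases (part d). They cannot all be followed for a transient flush that is listed in the consent form.

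**3. Timing.** Section 4 places soreness, sweating and flushing at about 2 days. The call is on day 7. The open question in item i belongs to the study physician at each visit, and the first in-person follow-up is at 4 weeks. Section 3 describes the day-7 contact as a phone call between visits 1 and 2; Appendix I numbers it as Visit 2. It is therefore unclear whether the open question is put at day 7 or first at week 4.

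**4. Size, by assumption.** Inputs: n = 30 per arm (60 in Section 3.5.1; 30 per group in Appendix II); true rate p of a transient-type effect, 10% to 40% (assumed); persistent share s, 0% to 50% (assumed). Women counted under item i = n × p. Women counted if only persistent cases were kept = n × p × s.

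| p | item i | persistent only, s = 0 to 50% |
|---|---|---|
| 10% | 30 × 0.10 = 3 | 0 to 1.5 |
| 20% | 30 × 0.20 = 6 | 0 to 3 |
| 40% | 30 × 0.40 = 12 | 0 to 6 |

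The chance of at least one counted case in an arm is 1 − (1 − q)^30, where q is the counted rate. At p = 10% it is 1 − 0.90^30 = 0.96. With s = 25%, q = 0.025 and it is 1 − 0.975^30 = 0.53. The two rules agree only if s = 100%.

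**5. Effect on the comparison.** If the same share s is counted in both arms, the counted difference is s × (p1 − p0). For example, with assumed rates of 40% and 20% and s = 50%, a true difference of 20 percentage points is counted as 20% − 10% = 10 points. The difference shrinks towards zero.

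**The case against.** A reader might infer that the recorded adverse event rate depends on whether 3.5.5 or the Safety Monitoring Plan is followed. The documents do not support that. The list in 3.5.5 is introduced in terms that do not make it exhaustive, the section points on to the Plan, and nothing in it exempts a transient event from the log. Its persistence sentence speaks of reporting, and the next sentence speaks of events also going to the IRB, so it most naturally sets an escalation threshold. Item i then still requires every event to be logged. This stands, and it moves the problem from the definition of the log to how events are elicited and passed on.

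A reader might also infer that transient events would be removed selectively from the steroid arm. That is not shown. The same rule applies in both arms, with the injecting physician and the participant blinded, and soreness or a vasovagal reaction could also follow a saline-lidocaine injection.

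Ascertainment is not absent either. Section 3.5.4 invites reports throughout week 1, Section 3.5.5 provides round-the-clock contact, Section 3 describes the call as asking about side effects or adverse events generally, item i asks about the whole interval since the previous visit, and part b, item iv encourages reports of new or resolved events. Worsening pain may capture some soreness. The study forms in Appendix IV are not in the text, so a day-7 checklist may exist. These points limit the size of the concern. They do not supply a meaning for persistent, settle the IRB rule, or put the four missing effects on a named prompt.

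**Conclusion.** The inconsistency is real and modest in weight. Read together, the documents make item i the rule for the log. Two risks remain: that short-lived effects go unelicited or are treated as not worth noting, and that staff apply different IRB thresholds. Both arise in either arm. If such effects are more common with the steroid, as Section 4's wording suggests, undercounting would tend to narrow the apparent difference between arms; that is conditional, and it is not evidence of differential removal.

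The range of 3 to 12 women against 0 to 6 rests wholly on assumed rates and shares, and the second figure applies only if persistent cases alone were counted. Section 3.8 plans no adverse event analysis, and safety is not among the outcomes in Section 1.2, so the effect falls on later safety tabulations and not on the primary comparison.

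**What to change.** - **Recording.** State in Section 3.5.5 that part a, item i is the single adverse event definition for recording, and remove persistence as a condition on recording.
- **IRB reporting.** Reconcile Section 3.5.5, Section 4 and part d of the Safety Monitoring Plan into one separate reporting rule. Which threshold it should use is for the investigators and the IRB. If persistent is kept there, define it.
- **Elicitation.** Use one solicited checklist covering the effects named in Sections 3.5.4, 3.5.5 and 4 at the day-7 call and at each visit, with the start and stop dates that part a, item iii already requires. If Appendix IV already holds such a form, align it with this list.
- **Tabulation.** Add to Section 3.8 a table of each event by arm.

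The cost is a few wording changes and a checklist used at contacts already scheduled. More minor events will be logged, so tolerability will look slightly less favourable.

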3.5.6 Confidentiality

Following HIPPA guidelines, patient identifiable data will be coded to protect each patient’s identity. The data obtained from the patients will be entered onto electronic forms and imported into the database. We are familiar with using this technology from other studies. It is efficient to complete in a clinical setting and minimizes data entry errors. The data will be presented in peer reviewed manuscripts and other public presentations at the group level only. No individual patients will be identified.

3.6 Schedule of events

(Refer to Appendix I for schedule of events, Appendix II for study timeline and to Appendix IV for study forms, attached pdfs)

3.7 Sample size (Refer to Appendix III for calculations)

Protocol Version 4 – 03-06-2015

Sample size calculations are based on a 2-sided type I error rate of .05 and 80 % power. An additional 10% is added to account for loss to follow-up and for premature deliveries. Non-compliance is expected to be minimal given the short duration of the study medication intervention. The variance estimates are obtained from a previously reported RCT in pregnancy related PGP by Bastiaenen¹⁶. Approximately 50 participants will be needed to detect 2-point NRS effect size for 25 (exp) compared to 25 (control).

3.8 Analysis

Data will be analyzed using descriptive univariate statistics with STATA 11.0. In this population, there is evidence from current literature that pain and disability may not be normally distributed. If this is the case, the primary and secondary outcomes, pain and disability respectively, will be presented as median values and interquartile ranges. Comparisons between the intervention groups at follow-up will be performed using the Mann Whitney U test and change within groups from baseline to follow-up will be examined using the Wilcoxon signed-rank test. If data are sufficiently normally distributed and differences are found, multivariate analyses will be conducted. This will determine the need to control for group differences based on location of pain, history of low back pain or pelvic girdle pain, age, educational level, parity, and time from pain onset. Additional secondary analyses will examine the impact of the treatment group assignment on physical examination tests using chi-square test of proportions.

4. Risks and Benefits

The excellent overall safety and efficacy record of injectable corticosteroids is well established²⁶. A prospective evaluation of intraarticular and periarticular injections with methylprednisolone found a very low rate of complications²⁷. Systemic effects of injectable corticosteroids are influenced by the agent used, dose, frequency and number of sites injected. Osteoporosis is found only with use of systemic/oral steroids and myopathy more commonly documented with oral fluorinated steroid use has not been reported with intraarticular injections. The ability of intraarticular injections to suppress the hypothalamic-pituitary-adrenal (HPA) axis

Protocol Version 4 – 03-06-2015

is well documented²⁸ but has not been described with extraarticular or ligamentous injections. A corticosteroid induced increase in glucose synthesis is not seen in soft-tissue injections of methylprednisolone acetate²⁹.

Fetal Risk and Benefit

Glucocorticoids constitute one of the most frequently prescribed medications during pregnancy, used commonly in preeclampsia and for maternal inflammatory, dermatologic, and autoimmune disorders. Antenatal glucocorticoids are used for a multitude of reasons in pregnancy. Examples of use are asthma refractory to inhalant therapy (*National Asthma Education and Prevention Program: Full Report of the Expert Panel: Managing asthma during pregnancy: Recommendations for pharmacologic treatment – 2004 update. NHLBI, NIH publication no. 005-3279I*), autoimmune disorders^{22,23} and for acceleration of fetal lung maturity for women at risk of preterm birth²⁴.

Although fluorinated glucocorticoids are known to cross the placenta readily, the majority of prednisone and methylprednisolone (non-fluorinated glucocorticoids) are inactivated in the placenta and do not reach the fetus in significant concentrations. Both of the latter are Category B agents in that animal studies show no risk but no definitive studies in humans have been done, and may be safely used as anti-inflammatory/immunosuppressive agents if indicated in pregnancy²⁵.

In light of this, the investigators feel that there is minimal risk to the fetus. Fetal exposure to systemic corticosteroids in pre-term labor and been proven safe and even advantageous to fetal lung maturity. There is no benefit in this study to the fetus aside from the potential long term benefit of better maternal pain control in the postpartum period that would influence maternal-child bonding and childcare.

Maternal Risk and Benefit:

The risk to the mother is also minimal. Mothers with moderate to severe pain have significant disability that affects current and future quality of life. The potential benefit of the pain
Protocol Version 4 – 03-06-2015

treatment outweighs the minimal risk. Both study groups will receive standard of care physical therapy (cost covered by their insurance), a proven treatment for pregnancy related pelvic girdle pain. For the intervention group that receives methylprednisolone, expected immediate side effects might include vasovagal reaction and delayed (2 days) side effects might include injection site soreness, sweating or facial flushing³⁰. Toxicity at high levels and multiple dosing effects are not expected given that this is a low dose of corticosteroid injected locally. Infection rates associated with injection are low and typically seen in intraarticular not extraarticular injections³¹. A possible rare adverse effect might include allergic reaction. If an adverse reaction or side effect occurs, the subject will be seen by [name] (maternal fetal medicine) at Loyola. This will also be immediately reported to the IRB.

The benefits of the intervention include the possibility of superior pain relief compared with placebo. Lidocaine has been safely and successfully used in pregnant women undergoing amniocentesis.³² Oral steroids are used for other conditions in pregnancy such as asthma, rheumatoid arthritis, and severe sinusitis. They are also utilized in the treatment of pre-term labor to assist in the development of fetal lung maturity. Methylprednisolone is a class B drug and its well-established clinical utility in other diseases lends to the safety of its potential use in this debilitating pain condition (PGP) in pregnancy and warrants further study for the treatment of musculoskeletal pain.

I. Safety Monitoring Plan

a. Definition of adverse events, serious adverse events

- i. An adverse event is defined as any symptom or medical problem experienced by the participant following consent to participate. All adverse events must be reported to the study physician and regulatory coordinator within three working days of discovery. All adverse events that occur during the trial will be recorded on the adverse event log. The investigator study physician will ask patients at each visit "Have you experienced any

symptoms or medical problems since your last visit?” and will subsequently record all events using the adverse event log.

- ii. Serious adverse events must be reported to the University’s IRB, Principal Investigator, Study Physician, and Regulatory Coordinator within 24 hours of discovery using the Serious Adverse Event Case Record Form. An SAE is defined as any adverse drug experience that results in:

1. Death
2. A life-threatening adverse experience
3. An important medical event
4. Inpatient Hospitalization (or prolonged hospitalization)
5. Persistent or significant disability/incapacity
6. A congenital anomaly or birth defect

- iii. Finally, the principal investigator or her designee will record on the adverse event log: (1) A description of the event, (2) the start date of the event, (3) the stop date of the event, (4) the expected relationship to the study drug, (5) Whether any action was taken with the study drug, and (6) the primary outcome of the event. Additionally, the principal investigator or her designee will record any change in an ongoing adverse event.

b. What procedures will be used to monitor subject safety?

- i. All participants will complete a general physical examination prior to randomization. Data will be recorded using the General Physical Case Record Form.
- ii. Vital signs (weight, height, temperature, seated blood pressure, and seated heart rate) will be taken at each visit. Data will be recorded using the Vitals Case Record Form.

- iii. [Description of labs used to monitor mother and child health, and how often those labs will be collected and evaluated. Also describe whether the participant will receive a copy of their laboratory results, and whether such a report will be given directly to them or sent to their personal healthcare provider].
 - iv. Participants are encouraged to report any (1) New adverse event, (2) whether any existing adverse events have worsened or resolved, (3) whether there are any changes to their concomitant medications, and (4) whether a medication was required to treat an adverse event. Such information is recorded on the adverse event log CRF and concomitant medication log CRF as necessary.
- c. Who (list names) will identify, document, and report adverse events?**
- i. All named research members may receive information about an adverse event and, consequently, are required to report such events as described in this protocol.
 - ii. The principal investigator and/or study physician will evaluate (1) The expected relationship of the event with the study drug and (2) Whether any action should be taken regarding the study drug following an adverse event.
- d. What is the frequency for review of summarized safety information and who will perform the review (e.g., safety monitoring board)?**
- i. The Principal Investigator or her designee will alert Loyola University Chicago Health Sciences Division IRB#1 *promptly* of all serious and any unexpected adverse events associated with the project (or the study supplement). **Associated** is defined as any adverse experience that is *possibly, probably, or definitely* related to the study drug. **Unexpected** is

defined as any untoward experience following informed consent that is not listed as a risk in the informed consent document.

ii. The Principal Investigator will also *promptly* report non-compliance with the activities described in the protocol, participant complaints, and any billing errors. Additionally, the PI will *promptly* report:

1. Serious adverse events (including events that produce injury or death, an event leading to hospitalization or lead to prolongation of a current hospital stay)
2. The enrollment of a patient on a study that is no longer enrolling participants
3. Any patient reporting a billing problem as a result of project participation
4. Any participant who has voiced a complaints about some aspect of the project or the consent document
5. Any unanticipated, untoward, or unexpected adverse event not covered above including rare adverse events or adverse events that occur at an unexpected rate
6. Protocol deviations
7. Investigational drug/device brochures and revisions

e. What are the stopping rules with regard to efficacy and safety?

- i. A decision to stop the study may be made when there are documented serious maternal or fetal adverse events that can be possibly, probably, or definitely attributed to study drug exposure and are deemed to exceed the potential benefits of the study drug.
- ii. The principal investigator, the Institutional Review Board, or United States Government Regulatory Authorities (e.g., the Federal Drug Administration or

FDA) may stop this study at any time. If this happens, the research team will be in direct contact with the Institutional Review Board and regulatory agency regarding participants' suspension or termination of study drug.

- iii. The investigator may decide to stop a subject's participation in this trial at any time. This may happen, for example, if the participant fails to comply with the protocol activities or experiences an adverse event. If this happens, the research team will be in direct contact with the Institutional Review Board and will, with the participant's informed consent, continue to follow the participant off study drug for pregnancy outcome and fetal adverse events.

5. Importance of Clinical Research in Pregnant Women

In October 2010, the Office of Research on Women's Health (ORWH) convened a scientific research forum, *Issues in Clinical Research: Enrolling Pregnant Women* in partnership with several National Institutes of Health (NIH) institutes, centers, offices and the Food and Drug Administration (FDA), to address the ethical/ Institutional Review Board (IRB) and recruitment issues that investigators face in the conceptualization, initiation, and conduct of clinical research studies that enroll pregnant women. During this forum, the audience was challenged to address gaps in knowledge about medical treatment and pregnancy, to increase the evidence base on the inclusion of pregnant women in clinical research, and to conduct appropriate scientifically- and ethically-designed clinical research. Medical ethicists, clinical investigators, academic researchers, and those with an interest in and concern about clinical research in women provided information related to risk perception, risk reasoning, and the ethics of balancing risks and benefits in the clinical arena.

The NIH strategic plan for research on women's health identified six major goals for women's health research, one of which was the goal of increasing research to "*actualize personalized prevention, diagnostics and therapeutics for girls and women.*" Among specific

objectives listed for the goal were two objectives that directly addressed pregnancy: 1) *“encourage research on safe and effective interventions for conditions affecting pregnant women”*; and 2) *“expand research on pregnancy related conditions, such as preeclampsia, diabetes, and hypertension on the subsequent health of women and their offspring.”*

The report from this forum (<http://orwh.od.nih.gov/resources/policyreports/pdf/ORWH-EPW-Report-2010.pdf>) made several poignant statements relevant to [name] proposed project.

- “The current approach to treatment during pregnancy has resulted in significant knowledge gaps and harms. Pregnant women are left with two unacceptable options: either take a drug of unknown safety and efficacy or fail to treat a condition, with consequences. Pregnant women deserve better.”
- “Only 12 drugs are explicitly approved by the FDA for use in pregnancy. These drugs are approved either to prevent premature labor or to ameliorate labor pain. All medicines used for non-obstetrical treatments with pregnant women are off-label. Pregnancy is the ultimate off-label condition. This lack of knowledge has led to a profound reticence to treat pregnant women when they do fall seriously ill, and it ends up harming the women and the babies.”
- “What is needed in the case of pregnancy research is the development of a thoughtful, careful framework to address a scientifically and ethically challenging situation.”

The PI ([name]) and co-investigators of this proposed project (Drs. [name], Loyola chief of maternal fetal medicine) and [name] (scientific collaborator and international expert in pregnancy related PGP RCTs) feel strongly that the proposed study addresses a significant issue in pregnancy: disabling pelvic girdle pain that can lead to deleterious maternal consequences if left untreated. We feel the injectate proposed is safe and with ultrasound guidance will pose minimal risk to the mother and fetus. The potential significant maternal

Protocol Version 4 – 03-06-2015

benefit outweighs this minimal risk. The proposed study also is in response to the NIH call to action for clinical research in pregnancy. The study has already been peer reviewed by the American Academy of Physical Medicine and Rehabilitation Foundation and, given its potential significant scientific contribution, has already been funded with recruitment to start in 2014.

